| Roles and Responsibilities | Principal Investigator: [name] MD, responsible for study design, overall project oversight, and compliance. Study Coordinator: [name], responsible for daily operation, protocol adherence and patient coordination at Kaizo Health Centers. [name] assisted [name] with initial study design, ongoing recruitment recommendations, pain measure decision-making, study flow creation. [name] PhD (Deceased), responsible for initial power analysis, statistical support for study design, revisions after FDA. [name] PhD, responsible for programming of data collection instruments, ongoing support of data collection tool and dataset, database consolidation; [name] PhD, responsible for statistical analysis of completed dataset. All apart from [name] reviewed the manuscript. |
| Introduction | Low back pain (LBP) affects nearly 40% of adults, contributing to significant reductions in quality of life and productivity. The opioid epidemic, largely driven by prescriptions for pain, has created an urgent need for effective non-pharmacological pain treatments. Existing options such as TENS devices may provide acute relief, but are not available as an opioid substitute. A multimodal approach, combining mechanical stimulation, heat, cold, and acupressure, holds promise for reducing both acute and chronic pain and opioid prescribing. |
| Background and rationale for the study | Between 25 and 50% of patients presenting with acute or exacerbated chronic LBP (a/cLBP) receive prescriptions for opioids. ALBP progresses to chronic in 40% of those with moderate to severe pain (4 out of 10 on a 0 – 10 Numeric Rating Scale). Opioid pain relief is no better than placebo at 6 weeks after presentation, but increases the risk of cLBP and persistent use (5% of opioid naïve). Providing a multimodal low back pain device could reduce opioid prescribing or use compared to TENS; providing any device could reduce opioid prescribing and use compared to contemporaneous prescribing practices. |
| Objectives | Primary Objective, Opioids: To determine whether the use of a multimodal neuromodulatory mechanical stimulation (M-Stim) device (DuoTherm) can reduce opioids 30% compared to TENS in those with moderate to severe back pain. |

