| Study Design | Co-Primary Objective, Acute Pain: To determine whether multimodal M-Stim reduces Pain Intensity 30% more than TENS in the first 10 days after presenting for treatment. Co-Primary Objective, Chronic Pain: To determine whether multimodal M-Stim reduces disability 30% more than TENS at 6 months. A randomized, double-blind controlled trial with 3- (aLBP) or 6- month (cLBP) follow-up. |
|-------------------------|--|
| Study Setting | The study will be conducted at mixed physical therapy/chiropractic practices in Washington, DC, Maryland, and Virginia, which offer demographic and economic diversity. These clinics provide an ideal environment, with frequent follow-ups and ongoing therapy but no onsite access to opioid prescribers. |
| Eligibility Criteria | Inclusion Criteria: - Male or female adults aged 18-90 presenting for treatment of acute or chronic low back pain - Self report of moderate to severe LBP of 4 or greater out of 10 on a 0-10 Numeric Rating Scale. - Acute: pain duration <3 months not using opioids for the current exacerbation of low back pain - Chronic: Pain duration >= 3 months with or without ongoing opioid use - Capacity to understand risks and benefits (informed consent). - Smartphone for Qualtrics web-based platform use Exclusion Criteria: - Radicular pain likely reflecting a surgical or mechanical problem - Inability to apply or use the device - Sensitivity to cold or vibration (e.g Raynaud's or Sickle Cell Disease) - Diabetic neuropathy rendering a patient unable to determine if the device is too hot - New neurologic deficits, skin lesions over the low back area - A contraindication to any medication for pain management that would impact analgesic use record |

| | - Pacemaker |
|--------------|---|
| Intervention | The experimental arm DuoTherm is a novel multimodal low back pain relief device incorporating 8 harmonic vibration patterns of mechanical stimulation (M-Stim) including neuromodulatory frequencies, 5 intensity levels, and optional heat, cold, and pressure delivered through a sculpted metal plate attached with a belt and controlled by buttons on the belt. Patients will be instructed to use the device at least daily for 30 minutes. The active control is a prescription 4-lead 8-channel TENS unit (LG Smart) with variable intensity. |

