| | Participants will be instructed to use the device for a minimum of 30 minutes a day. Both M-Stim and LG Smart TENS groups will receive a standard pain management regimen typically used for low back pain standardized across all clinicians participating in the study. Participants will keep the devices and be instructed to use them for pain as needed during the duration of the study. |
| Outcomes | Opioid Use Primary Outcome: |
| | Prior use: For patients with prior or ongoing opioid use, a 30% reduction in MME (Milligram Morphine Equivalents) between the first 14 days and the last 14 days of daily diary recordings using the DOSE data collection tool. |
| | Opioid naïve: 30% reduction of those receiving an opioid prescription "prescribed to me for this event" |
| | Secondary outcomes: Use days; total MME and use past 7 days in the opioid naïve; use days by those with more severe pain using the NIH Research Taskforce definitions; and prescribing compared to a contemporaneous national LBP population (25%). |
| | Pain Primary Outcome: |
| | Chronic: 30% lower disability at 6 months using PROMIS Pain Interference for those with ongoing pain >3 months |
| | Acute: 30% lower NRS 0-10 "pain now" from entry to 10 days for those presenting with an episode of pain starting within the past 2 weeks |
| | Secondary Outcomes: Change in disability for those with >=57.7 PROMIS Pain Interference; restoration of function to normal (PI=50); |

| | integrated analysis with | n common | criteria fo | r restoration | on of function | on with | |
|-------------------------|---|---------------|--------------------|---------------------|----------------------|----------------------------|--|
| | multifidus stimulation s | surgery. | | | | | |
| | | | | | | | |
| Participant Timeline | | Initial Visit | Daily x 28 days | Weekly for 3 months | Monthly for 3 months | Monthly 4 - 6 months | |
| | Consent, Enrollment, Randomization | ALBP, CLBP | | | | | |
| | Minimum Dataset, Pain Catastrophizing Sullivan, PROMIS Depression, Physical Function | ALBP, CLBP | | | | | |
| | NRS (at that moment & past 24 hours) | ALBP, CLBP | ALBP, CLBP | ALBP, CLBP | ALBP, CLBP | CLBP | |
| | NRS after 30 minutes | ALBP, CLBP | | | | | |
| | NRS Past week | | | ALBP, CLBP | ALBP, CLBP | CLBP | |
| | NRS Past month | | | | ALBP, CLBP | CLBP | |
| | PROMIS Pain Intensity, Pain Interference | ALBP, CLBP | | ALBP, CLBP | ALBP, CLBP | CLBP | |

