| | Dose, Opioid formulation, number Source (DOSE tool), other analgesics | ALBP, CLBP | ALBP, CLBP | ALBP, CLBP | ALBP, CLBP | CLBP | |
| | Device usage | | ALBP, CLBP | ALBP, CLBP | ALBP, CLBP | CLBP | |
| Sample Size | To estimate the M-Stim | interventi | on effect : | size, a retro | spective st | udy of | |
| | 59 cLBP patients on ch | ronic opioi | ds (100% | prolonged | opioid use) | | |
| | reported a 28% reducti | on in MME | after spin | al stimulat | or | | |
| | implantation,[40] reducing MME 26.2(SD32.8) compared to 5.8(SD34.2) | | | | | | |
| | for those with conventional treatment (effect size 0.60. A priori, we would | | | | | | |
| | be able to detect an effect size of 1 (meaning a difference of 1 standard | | | | | | |
| | deviation) with 94% power and alpha of .03 using a Wilcoxon Mann | | | | | | |
| | Whitney test with 30 in each group. With this effect size for a two-sided | | | | | | |
| | significance of 0.05, 17 participants per group would detect a 30% | | | | | | |
| | prescribing reduction, while 50 participants on chronic opioids per | | | | | | |
| | treatment group would provide 85.4% power to detect a 30% reduction in | | | | | | |
| | MME. Given the 20% in a previous study by Jamieson et al, we increased | | | | | | |
| | the cLBP sample to 50 | - | | Jannoson | icat, we iiio | ioasea | |
| | | | | | | | |

| | We planned to recruit 60 aLBP participants who had never taken opioids for their back pain, and 100 cLBP without a new prescription but with or without chronic opioid for cLBP. |
|----------------------------|--|
| Recruitment | Patients were recruited from Kaizo Health Centers in Landover and Fairfax, through direct referrals, flyers, and digital content like social posts and emails targeting local populations. Flyers were also distributed at three local pain clinics. |
| Randomization | After eligibility screening and informed consent, a 4-digit participant ID and the intervention allocation were randomly assigned by the survey software to either the DuoTherm or LG Smart TENS group within acute and chronic arms. A copy of the informed consent was emailed to the participant. |

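### Comparing the trial's opioid prescribing with a fixed national rate of 25% cannot show that providing any device reduces prescribing

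*Combined protocol and SAP*

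**What the plan says.** All references are to the combined protocol and SAP.

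- **Outcomes** (secondary opioid outcomes): "prescribing compared to a contemporaneous national LBP population (25"%). No source, years, care setting or uncertainty is given for the figure.
- **Background and rationale**: "Between 25 and 50% of patients presenting with acute or exacerbated chronic LBP (a/cLBP) receive prescriptions for opioids". The same section adds that "providing any device could reduce opioid prescribing and use compared to contemporaneous prescribing practices".
- **Study Setting**: physical therapy and chiropractic practices, "with frequent follow-ups and ongoing therapy but no onsite access to opioid prescribers".
- **Eligibility Criteria**: "Acute: pain duration <3 months not using opioids for the current exacerbation of low back pain". Chronic patients may enter whether or not they currently use opioids. Exclusions include "Radicular pain likely reflecting a surgical or mechanical problem".
- **Sample Size**: the planned sample was "60 aLBP participants who had never taken opioids for their back pain, and 100 cLBP without a new prescription".
- **Intervention**: each arm receives a device plus the same pain-management regimen.
- **Statistical Methods**: prescribing differences are summarised as raw percentage change and relative risk. Nothing is said about a test, analysis set, matching, adjustment or caveat for the comparison with 25%.

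**The concern.** A claim about any device needs a group without a device, and the trial has none. The fixed 25% has to stand in for it. That is valid only if patients like these, in these clinics and under the same regimen, would have been prescribed opioids at 25% without a device. The documents themselves give several reasons to doubt this.

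If the clinics' underlying rate is below 25%, the trial will look favourable even when neither device does anything, and a larger sample makes the false signal more certain. At stake is a secondary claim that the devices lowered prescribing relative to national practice, when the difference could come from setting, selection and co-treatment.

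**Working it through.** **The plan's own figure.** The 25% is asserted, not derived, so there is nothing to reproduce. The sample-size calculations concern the randomised arms and do not bear on this comparison.

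**Comparability, from the documents.**

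| Feature | Section | Likely effect on trial prescribing relative to 25% |
|---|---|---|
| No opioid prescriber on site | Study Setting | Lower |
| Acute patients using opioids for the episode excluded | Eligibility Criteria | Lower |
| Chronic patients planned to have no new prescription | Sample Size | Lower |
| Radicular pain of likely surgical or mechanical origin excluded | Eligibility Criteria | Lower |
| Common regimen and ongoing therapy in both arms | Intervention; Study Setting | Probably lower; cannot be separated from the device |
| Pain of at least 4 on the 0-10 scale required | Eligibility Criteria | Higher |
| Flyers at three pain clinics | Recruitment | Higher |
| Ongoing opioid use allowed in chronic patients | Eligibility Criteria | Higher |
| Follow-up of 3 or 6 months | Study Design | Higher, with more time for a prescription |

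The directions are judgements. The features themselves are in the documents.

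**Illustration of size.**

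Inputs:
- Benchmark 25% (Outcomes).
- n = 60, the planned acute sample (Sample Size).
- n = 80, an approximation to the opioid-naive patients: Protocol Amendments reports that half of each stratum had no prior opioids for back pain, and (60 + 100)/2 = 80.
- Assumed, because the plan gives neither: a two-sided exact binomial test at 0.05, and the clinics' background rate b with both devices inert.

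Rejection limit: the largest count k below expectation with exact p ≤ 0.05 under 25%.
- n = 60: k = 8 (p = 0.037; 9 events give p = 0.075).
- n = 80: k = 12 (p = 0.039; 13 events give p = 0.072).

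Probability of a significantly lower result = P(X ≤ k), with X ~ Binomial(n, b):

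| Background rate b | n = 60, P(X ≤ 8) | n = 80, P(X ≤ 12) |
|---|---|---|
| 5% | 99.7% | >99.9% |
| 10% | 86% | 95% |
| 15% | 44% | 58% |
| 20% | 13% | 16% |
| 25% | 2% | 2% |

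The error is held near its nominal lower-tail level only if b really is 25%.

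**Contrast with the randomised comparison.** With both devices inert, a Fisher exact test between arms (30, 40 or 80 per arm, b from 5% to 20%) is significant in at most 3.2% of trials. Setting and selection apply equally to both arms, so this comparison keeps its error control whatever b is.

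**The case against.** The strongest reply is that the point attacks something the plan does not do. The comparison is one secondary outcome. The sentence about any device is a possibility raised in the Background and is not an objective. The primary opioid objective is already DuoTherm versus TENS. No test or decision rule against 25% is written, and 25% is the low end of the plan's own 25-50% range, which makes a favourable result harder to reach. All of this is correct. It limits the reach of the point and means that the binomial test is only an illustration. It does not make the populations comparable, and a raw percentage or relative risk against 25% would carry the same confounding with no error control stated.

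The documents do not support four stronger inferences that a reader might draw:

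- **That a device benefit would be concluded even if neither device works.** This depends on the background rate, which is not given. At 20% the chance is 13% to 16%, and at 25% about 2%.
- **That the 25% describes general care.** The documents say only that it is a national low back pain population.
- **That the absence of an on-site prescriber means no prescribing.** The outcome counts prescriptions for this event without limiting them to the clinic.
- **That all current opioid users are excluded.** Only acute patients using opioids for the present episode are; chronic patients may be on opioids.

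**Conclusion.** The concern holds in a limited form. The comparison with 25% is non-randomised, confounded by setting, entry criteria and co-treatment, and carries no caveat, so it cannot support a conclusion that providing any device reduces prescribing. Lack of comparability follows directly from the documents. The net direction is likely downward but not established, because several features could raise prescribing.

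The size rests on two assumptions, the exact test and the background rate. Across rates of 5% to 25%, the chance of a spurious finding runs from near certainty to about 2%. The documents do not show where these clinics lie in that range. The effect is confined to one secondary outcome and the statement it feeds.

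**What to change.** In Outcomes and Statistical Methods:

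1. Label the comparison descriptive. Name the analysis set, and report the trial's prescribing rate with a 95% CI.
2. State that no conclusion about the devices relative to national practice will be drawn from it. Base the prescribing conclusion on the randomised M-Stim versus TENS contrast.
3. Beside the 25%, give its source population, the clinic setting, the exclusion of acute patients using opioids for the current episode (not of all current users), and the other differences in both directions.

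This changes wording only and needs no new data. The cost is the loss of a favourable-looking secondary claim. A causal statement about any device would need a concurrent group without a device, or a cohort from the same clinics under the same entry criteria.

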Participants recorded when they used their device, duration of use, and any additional pain relief modalities (exercise, stretching, bath, hot tub, therapy, massage). Patients were asked to record any thermal use or therapy cycle or channel as appropriate to their device.

Participants verbally endorsing pain for less than three months (acute) were entered into a 3 month follow-up program, or 6 months (chronic) for those for whom back pain had been an ongoing problem for more than 3 months.

Statistical Methods

Statistical analysis was performed with masked intervention allocation by a statistician new to the project to determine differences in primary and secondary outcomes.

An intention-to-treat analysis included all participants meeting inclusion criteria. Summary statistics (means, standard deviations, proportions) were calculated using T-tests and Chi-squared tests. Opioid prescribing differences were calculated with raw percent of change and relative risks. Diary entries and item-level data were analyzed for missing data to assess the need for imputation. Relative risks were calculated for MME and opioid use days between intervention groups, with paired T-tests used to compare first two and last two weeks of MME in those who used opioids during the study. A linear regression assessed BMI's interaction with opioid use, calculating marginal effects with standard errors via the Delta Method. Data analysis was performed using STATANow/SE 18.5.

For pain outcomes, in addition to the above methods, missing 10 day NRS-1 data will be imputed using forward fill and KNN. A neural network will be created to determine factors contributing to 13 week Pain Interference, with iterative modeling to reduce mean absolute error. Graphs with r-squared for predictors will be generated.

| Data Monitoring | Data collection was conducted through an app that tracked daily pain, opioid use and device usage. Monitoring included weekly enrollment review by the protocol statistician to assess comprehension of the data collection tool. Adverse events were reported as per protocol. | |
|------------------------|---|--|

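### The chronic 6-month co-primary has no estimator beyond a general T-test and no missing-data method, so by default the earlier Pain Interference scores go unused

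*Combined protocol and SAP*

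**What the plan says.** The co-primary objective for chronic pain (Study Design row) is "To determine whether multimodal M-Stim reduces disability 30% more than TENS at 6 months". Outcomes gives the endpoint as "Chronic: 30% lower disability at 6 months using PROMIS Pain Interference for those with ongoing pain >3 months".

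Statistical Methods holds everything said about analysis:

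- The general test: "Summary statistics (means, standard deviations, proportions) were calculated using T-tests and Chi-squared tests". The pain paragraph carries the preceding methods over to pain outcomes.
- The population: "An intention-to-treat analysis included all participants meeting inclusion criteria".
- Missing data in general: "Diary entries and item-level data were analyzed for missing data to assess the need for imputation".
- Missing data for a named pain endpoint: "missing 10 day NRS-1 data will be imputed using forward fill and KNN". This is the acute endpoint.
- The only model that names Pain Interference: "A neural network will be created to determine factors contributing to 13 week Pain Interference".

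In Participant Timeline, the row "PROMIS Pain Intensity, Pain Interference" is marked at the initial visit, weekly for 3 months, monthly for 3 months, and monthly in months 4 to 6 for chronic participants. The 6/8/2022 amendment also has it weekly to 3 months. Data Collection Methods instead has it added at the monthly surveys.

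**The concern.** Month 6 is the end of the longest follow-up, and the data come from self-completed web surveys, so some scores will be missing. A T-test cannot use a participant who has no month-6 score. Unless something else is specified, the comparison falls back on those who answered, and the earlier scores of everyone else play no part.

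Two things are at stake. One is precision, because earlier scores carry information about the missing ones. The other is bias: if the relation between pain and leaving differs by arm, the remaining participants are selected differently in each arm. That is plausible here. Participants know which device they have once the first pain rating is recorded, and a vibrating belt with optional heat and cold is a different experience from electrodes. It also matters that the method is open. Choosing how to handle missing co-primary data after seeing them weakens the claim that the analysis was planned.

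**Working it through.** **1. Which stated methods could apply to month-6 Pain Interference?**

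| Method in Statistical Methods | Tied to | Arm contrast at month 6? |
|---|---|---|
| T-test | summary statistics, general | yes, by default |
| Chi-squared test | proportions | not for a mean score |
| Relative risk | opioid outcomes | no |
| Paired T-test | MME, first versus last two weeks | no |
| Linear regression | BMI and opioid use | no |
| Forward fill and KNN | day-10 NRS | no |
| Neural network | predictors of 13-week Pain Interference | no |

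Only the T-test remains, and no planned arm comparison uses the repeated scores.

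**2. The plan's own figure.** Sample Size gives MME reductions of 26.2 (SD 32.8) and 5.8 (SD 34.2). Pooled SD = sqrt((32.8² + 34.2²)/2) = 33.51, and d = 20.4/33.51 = 0.609. With 50 per group and two-sided 0.05, T-test power is 85.4%, as stated. This concerns MME, so it neither supports nor refutes the present point. For scale only: at that effect size, 40 per group gives 76.7%.

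**3. Assumed inputs.** 50 per arm (planned chronic sample of 100, taken as 1:1). Assumed, because the documents give no values: SD 7 T-score points; 20% lost by month 6; correlation r between month 3 and month 6 of 0.6 to 0.75; dropout logistic in the month-3 score, with odds ratio (OR) 1.6 to 2.7 per SD.

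**4. Precision under random loss.** In units of SD²/n, the variance of an arm mean is 1/0.8 = 1.25 with available cases, and r² + (1 − r²) × 1.25 when the month-3 score is used.

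- r = 0.6: 0.36 + 0.64 × 1.25 = 1.160; ratio 1.25/1.160 = 1.08.
- r = 0.75: 0.5625 + 0.4375 × 1.25 = 1.109; ratio 1.25/1.109 = 1.13.

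These are large-sample values. Simulations at 50 per arm give about 6 to 13%.

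**5. Bias of the available-case difference.** Let z be the standardised month-3 score, p(z) the dropout probability and b = ln(OR). Among those who stay, mean z = −b × E[p(1 − p)]/0.8, and the month-6 mean shifts by 7 × r × that value.

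| OR | b | E[p(1 − p)] | mean z, stayers | shift, r = 0.6 | shift, r = 0.75 |
|---|---|---|---|---|---|
| 1.6 | 0.470 | 0.1545 | −0.091 | −0.38 | −0.48 |
| 2.0 | 0.693 | 0.1487 | −0.129 | −0.54 | −0.68 |
| 2.7 | 0.993 | 0.1388 | −0.172 | −0.72 | −0.91 |

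- Same relation in both arms: the shifts cancel and bias is 0.
- Informative in one arm, OR 2.0 to 2.7: 0.54 to 0.91 points.
- Opposite directions, OR 1.6 to 2.7: twice the shift, 0.76 to 1.81 points.

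**6. Type I error.** With 40 left per arm, SE = 7 × sqrt(2/40) = 1.565. With k = bias/SE, the rejection rate is Φ(−1.96 + k) + Φ(−1.96 − k).

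- One arm: k = 0.35 to 0.58, giving 6.4% to 8.9%.
- Opposite: k = 0.49 to 1.16, giving 7.8% to 21%.

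**7. Simulation check** (50 per arm, no true effect, 8,000 runs per setting). One arm: bias 0.55 to 0.93, error 6.4 to 8.8%. Opposite: 0.77 to 1.79, error 7.3 to 21.4%. Alike in both arms: bias within 0.03, error 4.8 to 5.0%. Regression on the month-3 score left bias within 0.04 in every setting.

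A separate large-sample run used monthly scores, dropout depending on the previous score, 20 to 26% loss and a true difference of −3.0. Available cases gave −1.8 under opposite-direction loss and −2.5 under loss related to pain in TENS only. A method using all earlier scores gave −3.0 in both.

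**The case against.** A reader might infer that the plan prescribes a T-test in month-6 responders only. It does not. The T-test appears in a sentence on summary statistics and is not tied to this endpoint, the analysis is called intention-to-treat, and a check on the need for imputation is stated. What is wrong is that the method is left open, not that a responders-only analysis was chosen. The two provisions do not close the gap, though: an intention-to-treat label does not say how a missing score enters a T-test, and the imputation check names neither a method nor a rule. The same section does name a method for day 10, so the omission for month 6 is plain.

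A reader might also infer that dropout related to pain biases the comparison in itself. When the relation is the same in both arms, bias is about zero and the error rate is nominal.

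Three further points stand. Every input for the size of the bias is assumed. The good performance of the model in step 7 is partly built in, because dropout there depends only on scores that were observed. The documents do not say when participants leave, so someone lost early may have few scores after baseline, or none if the monthly schedule is the true one. Finally, multiple imputation from the same earlier scores would serve as well as a mixed model; what matters is that one of them is named in advance.

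**Conclusion.** The point holds as a gap in specification, with a better method at hand on data already scheduled. For this co-primary the plan supplies only a general T-test and no missing-data method. The certain consequence, if that default is used, is that earlier scores are discarded. The variance cost under random loss is modest, at about 6 to 13%.

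Bias is conditional on pain-related loss differing between arms: about 0.5 to 0.9 points with type I error of about 6 to 9% if it occurs in one arm, and about 0.7 to 1.8 points with 7 to 21% if it runs in opposite directions. These ranges rest on the assumed SD of 7, 20% loss, correlations of 0.6 to 0.75 and the stated odds ratios. The documents show neither that such loss occurred nor which arm it would favour. The change should be made, but the documents do not support saying that the result is biased.

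**What to change.** In Statistical Methods, name the primary analysis of the chronic co-primary:

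- The month-6 M-Stim minus TENS contrast from a mixed model for repeated measures on the monthly Pain Interference scores, months 1 to 6, with unstructured covariance. Fixed effects: baseline Pain Interference, arm, month and arm-by-month. Multiple imputation from the same scores is an acceptable equivalent.
- Population: all participants randomised in the chronic stratum with at least one post-baseline score. Report by arm how many have none. No stratum term is needed: randomisation was within the acute and chronic strata, so it is constant in this set.
- One delta-adjusted sensitivity analysis, with missing month-6 scores shifted by a stated range that may differ by arm.
- How the mean contrast maps to the 30% criterion in the objective and outcome.
- The position of acute-stratum enrollees with longer pain duration. Protocol Amendments reports 16 of 60. They were placed on 3-month follow-up, so they have no month-6 score by design and should not be counted as dropouts.
- Which Pain Interference schedule to 3 months applies, since the weekly and monthly descriptions conflict.

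The cost is SAP wording and slightly more analysis work, with a standard model and no new data. The model assumes that scores are missing at random given those observed, which the sensitivity analysis probes. If month-6 results by arm have already been seen, the text should say so.

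### The acute pain co-primary is limited, without explanation, to episodes that began within 2 weeks, so eligible acute participants with 2 weeks to 3 months of pain have no pain co-primary outcome

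*Combined protocol and SAP*

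**What the plan says.** All places are in the combined protocol and SAP.

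- **Outcomes, Pain Primary Outcome, acute:** a 30% lower 'pain now' score "from entry to 10 days for those presenting with an episode of pain starting within the past 2 weeks".
- **Outcomes, Pain Primary Outcome, chronic:** "30% lower disability at 6 months using PROMIS Pain Interference for those with ongoing pain >3 months".
- **Objectives, acute pain co-primary:** "To determine whether multimodal M-Stim reduces Pain Intensity 30% more than TENS in the first 10 days after presenting for treatment". It is labelled acute pain and states no duration.
- **Eligibility Criteria:** "Acute: pain duration <3 months not using opioids for the current exacerbation of low back pain".
- **Randomization:** allocation by the survey software "to either the DuoTherm or LG Smart TENS group within acute and chronic arms". No 2-week stratum is mentioned.
- **Data Collection Methods:** "Participants verbally endorsing pain for less than three months (acute) were entered into a 3 month follow-up program".
- **Statistical Methods:** an intention-to-treat analysis of all participants who met the inclusion criteria.
- **Sample Size:** 60 acute participants planned. A generic statement gives 94% power for a 1 SD effect at alpha 0.03, by Wilcoxon-Mann-Whitney, with 30 per group. No number is given for a 2-week subset.
- **Protocol Amendments, on stratification:** once enrolment was complete, 16 of the 60 in the acute stratum were found to have reported more than three months of pain, and the data were pooled.

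**The concern.** Two definitions of the acute population are in use. Eligibility and follow-up, and with them the arms used for allocation, rest on the 3-month boundary. The co-primary outcome rests on a 2-week boundary that appears nowhere else and is not justified. The chronic co-primary starts at 3 months, so the band from 2 weeks to 3 months falls between the two pain outcomes.

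The set may also be open at the other end. 'Episode' is not defined, and eligibility itself speaks of a current exacerbation. A participant in the chronic stratum with a recent flare might therefore be counted. Two analysts could build different sets from this text.

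At stake are the size of the analysed set, its balance (allocation was not stratified on 2-week onset), and whether the result answers the acute objective.

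**Working it through.** **1. Who belongs to which pain co-primary, reading the text as written**

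| Participant | Acute co-primary | Chronic co-primary |
|---|---|---|
| Acute arm, onset within 2 weeks | yes | no |
| Acute arm, onset 2 weeks to 3 months | no | no |
| Chronic arm, no recent flare | no | yes |
| Chronic arm, recent flare | unclear, as 'episode' is undefined | yes |

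The second row is the gap. These people meet the inclusion criteria, so leaving them out of both pain co-primaries conflicts with the intention-to-treat statement. They still count for the opioid outcomes.

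**2. The plan's own power figure**

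Inputs from Sample Size: n = 30 per group, d = 1 SD, alpha 0.03, Wilcoxon-Mann-Whitney. Sidedness is not stated for the 0.03; two-sided is assumed.

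Method: multiply n by the Wilcoxon efficiency under normality, m = n × 3/π, then use the noncentral t distribution with df = 2m − 2, noncentrality d × √(m/2) and the two-sided critical value at 0.03.

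For n = 30: m = 30 × 0.955 = 28.65, df = 55.3, noncentrality = √(28.65/2) = 3.785, critical t = 2.228, power 93.7%. A simulation of the Wilcoxon test with 20,000 runs also gave 93.7%. The stated 94% is reproduced. Thirty per group corresponds to the full acute stratum, 60/2.

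**3. The same calculation with fewer participants**

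The share with onset within 2 weeks is not in the documents. The shares below are assumptions, applied to 60 acute participants split evenly.

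| Assumed share | n per group | m | Noncentrality | Power | Simulated |
|---|---|---|---|---|---|
| 100% | 30 | 28.65 | 3.785 | 93.7% | 93.7% |
| 75% | 22 | 21.01 | 3.241 | 83.5% | 83.2% |
| 50% | 15 | 14.32 | 2.676 | 65.1% | 62.6% |
| 25% | 8 | 7.64 | 1.954 | 34.9% | 28.9% |

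The approximation is somewhat generous at the smallest size.

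**4. The reclassified participants**

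16/60 = 27% of the acute stratum reported more than three months. Without them 60 − 16 = 44 remain, or 22 per group if they split evenly, with about 84% power on the same basis. This matters for the remedy: the acute arm as randomised and the set with reported duration under 3 months are not the same people.

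**The case against.** The other side has several sound points.

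- **A recent-onset population is defensible for a 10-day endpoint.** Onset is fixed at baseline, so restricting on it does not by itself bias the comparison. This stands. A reader might infer that the 2-week limit invalidates the treatment contrast; the documents do not support that.
- **The objective gives no duration.** A reader might take it to promise all pain under 3 months. It says only acute pain, and the 3-month rule comes from eligibility and follow-up. The Outcomes row could then be read as specifying an open term. That softens the conflict with the objective but leaves the conflict with the intention-to-treat statement and the gap between the two pain co-primaries.
- **No sample size for this endpoint was lost.** The Sample Size text concerns opioid outcomes, and its 1 SD statement names no endpoint. The printed effect size of 0.60 comes from reductions in morphine equivalents after spinal stimulator implantation in chronic opioid users, so it should not be used as a pain-score effect in acute back pain. This stands, and the table above is therefore only illustrative.
- **The denominator is uncertain.** If recent flares in the chronic stratum qualify, the analysed set is not simply a fraction of 60. Precision also depends on variance and effect being alike across onset groups, which the documents do not show. Both points stand. They limit the figures but also show that the set is undefined.

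**Conclusion.** The inconsistency is real and lies in the current text. The acute pain co-primary has an unexplained 2-week limit that leaves eligible, randomised participants with 2 weeks to 3 months of pain without a pain co-primary. It may also admit some chronic-arm participants. The consequences are lost precision, a set not protected by the stratification, and a finding narrower than the acute objective.

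It would be too strong to say that acute participants are dropped from the primary analysis in general: only this onset band is affected, and only for pain.

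The size cannot be fixed from the documents. On the plan's generic assumptions, power goes from about 94% with 30 per group to 65% with 15 and 35% with 8. This assumes two-sided alpha, a 1 SD effect that does not vary with onset, an even split, and an assumed share with recent onset. The direction is firm if the set is a subset of the acute arm; the amount is not known.

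**What to change.** Reconcile Objectives, Eligibility Criteria, Outcomes, Randomization, Statistical Methods (with the follow-up definition just before it) and the stratification note under Protocol Amendments, as follows.

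1. Make the acute pain primary set everyone randomised in the acute arm. Analyse 10-day 'pain now' adjusted for the initial 'pain now'. Describe that baseline as recorded before allocation was revealed to the participant. The Blinding section supports this; it does not show that the score preceded allocation itself.
2. Report onset within 2 weeks as a named subgroup, with a definition of episode.
3. Add a sensitivity analysis without the 16 of 60 who reported more than three months, leaving 44, about 22 per group.
4. Because enrolment is complete, date the change, disclose it, and make it without sight of results by arm.

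No new data are needed: the Participant Timeline schedules the daily pain score for acute and chronic participants alike. The costs are a more varied population, which the subgroup and sensitivity analysis address in part, and a late change to a co-primary population that has to be declared as such. If the sponsor prefers to keep the 2-week limit, the objective should state it, with the reason, the definition of episode, and the expected number and power.
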